7.2 Phase II Statistical Analysis Plan

This is an open label single arm Phase II study to test the hypothesis that the CR rate is less than or equal to 20% versus the alternative hypothesis that the CR rate is greater than or equal to 50%.

Our sample size estimate is based on our primary hypothesis that evaluates CR rate in the HL cohort. One-sided binomial tests will be used to assess these changes. Given a baseline CR of 21% for single agent pembrolizumab in relapsed HL, we hypothesize that combination of lenalidomide and pembrolizumab will have a CR rate of 50% or greater for the combination at a significance level of 0.05 with 80% power (PASS, 2008).

With 17 patients entered into this trial, with 83% power and alpha of 0.04, we can reject the null hypothesis if 6 or fewer responses are observed.

Patient and disease characteristics will be summarized at baseline using descriptive statistics (means, medians, quartiles, standard deviations, etc.) and graphical displays including boxplots for continuous variables and frequency distributions for qualitative variables.

The complete response rate will be estimated with exact 95% confidence intervals. Other secondary response measures will be summarized using frequency distributions. Distributions of dose and time on treatment will also be summarized. Time to failure will be estimated using Kaplan Meier methods (failures include progression or death, death). Descriptive summaries of response duration and transfusion independence duration will also be summarized using Kaplan Meier methods ²⁵.

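### The Phase 2 decision rule in Section 7.2 is reversed: it rejects the 20% null for 6 or fewer responses of 17, when only 7 or more can support rejection.

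*Combined protocol and SAP*

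**What the plan says.** Section 7.2 (Phase II Statistical Analysis Plan) sets out a single-arm test of "the hypothesis that the CR rate is less than or equal to 20% versus the alternative hypothesis" of a CR rate of at least 50%. On the method it says "One-sided binomial tests will be used to assess these changes". The benchmark is the single-agent result: "Given a baseline CR of 21% for single agent pembrolizumab in relapsed HL". The design target is set "at a significance level of 0.05 with 80% power (PASS, 2008").

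The attained operating characteristics and the rule share one sentence. It begins "With 17 patients entered into this trial, with 83% power and alpha of 0.04" and ends "we can reject the null hypothesis if 6 or fewer responses are observed".

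Section 3.1 gives the same direction of interest, since its Phase 2 hypothesis is a CR rate of 50%. No other section states a Phase 2 cut-off or corrects this one.

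**The concern.** The null is a low CR rate and the alternative a high one, so evidence against the null is a large number of CRs. The written rule instead places the rejection region at 0 to 6 of 17, the lower end of the scale. Six is in fact the largest count at which the null should be retained.

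This sentence is the only numerical success criterion for Phase 2. Followed literally, it would declare the combination active after no complete responses and inactive after 17 of 17. If instead the cut-off is put right only once results are known, in an open-label single-arm trial, nobody can show from the plan that the threshold was fixed in advance.

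**Working it through.** **Inputs, all from Section 7.2:** n = 17; null CR rate 20%; alternative 50%; single-agent benchmark 21%; one-sided binomial test; target alpha 0.05 and power 80%; stated attained alpha 0.04 and power 83%.

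**Formula.** With X the number of CRs among 17 patients and p the true CR rate, P(X = k) = C(17, k) p^k (1 − p)^(17 − k).

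**Step 1: reproduce the plan's alpha and power.** Find the upper-tail cut-off r for which P(X ≥ r) is about 0.04 at p = 0.20 and about 0.83 at p = 0.50.

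| Reject if | Alpha at 20% | Power at 50% |
|---|---|---|
| X ≥ 6 | 0.1057 | 0.9283 |
| X ≥ 7 | 0.0377 | 0.8338 |
| X ≥ 8 | 0.0109 | 0.6855 |

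Only X ≥ 7 fits. Its alpha rounds to 0.04 and its power to 83%.

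**Step 2: evaluate the rule as written, X ≤ 6.**

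At p = 0.20, the terms for k = 0 to 6 are 0.0225 + 0.0957 + 0.1914 + 0.2393 + 0.2093 + 0.1361 + 0.0680 = 0.9623.

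At p = 0.50, every sequence of outcomes has probability 1/2^17 = 1/131,072. The coefficients for k = 0 to 6 are 1 + 17 + 136 + 680 + 2,380 + 6,188 + 12,376 = 21,778, and 21,778 / 131,072 = 0.1662.

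The literal rule therefore rejects a true 20% null about 96% of the time and detects a true 50% rate about 17% of the time.

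**Step 3: link the two rules.** They are complements: 1 − 0.9623 = 0.0377 and 1 − 0.1662 = 0.8338. The stated alpha and power are exactly those of the opposite rule, which locates the error in the direction of the sentence and not in the calculation.

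**Step 4: check the sample size and the benchmark.** Searching upward in n for exact alpha of at most 0.05 and power of at least 80% (20% versus 50%), n = 14 reaches only 0.788, n = 15 0.696 and n = 16 0.773. The first n that qualifies is 17, with cut-off 7. Taking the 21% benchmark as the null, X ≥ 7 of 17 has alpha 0.0479, still below 0.05.

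**Step 5: can the planned confidence interval stand in for the rule?** Section 7.2 also plans an exact 95% interval for the CR rate. At 7 of 17 (41%) the two-sided exact interval is 18.4% to 67.1%. It includes 20% although the one-sided test rejects at that count, so the interval does not recover the success criterion.

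**The case against.** The strongest reply is that the slip is obvious and the intent can be recovered. The same section gives the hypotheses, the sidedness, n, alpha and power, and these determine the cut-off of 7 uniquely. A statistician who ran the specified test would reach the right conclusion whatever the sentence says. Nothing was miscalculated; most likely rejecting was written where failing to reject was meant. Section 7.2 attaches no stopping rule or interim look to the count, and Section 3.1 frames the Phase 2 objective as estimation. On this view a 96% type I error describes a literal reading and not how the trial would probably be analysed.

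Much of that stands: the design is sound, patient treatment does not depend on the sentence, and the literal outcome is unlikely to be acted on. It does not make the sentence acceptable. This is the only stated boundary for the formal test, and it contradicts its own hypotheses, alpha and power. A reader who repaired it by changing only the direction would arrive at 6 or more, with alpha 0.106, more than twice the 0.05 level. The exact number has to be in the text.

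Two related inconsistencies do not alter the finding but affect how the correction is worded. Section 2.1 gives 15 Phase 2 patients, while Sections 1.0, 7.1 and 7.2 give 17. At n = 15, X ≥ 7 has power 0.696 and X ≥ 6 has alpha 0.061, so neither meets both targets. Also, Section 3.1 names overall response (CR and PR) as the Phase 2 objective and Section 4.2.3.1 lists CR, ORR and PR, so the bare word for responses in the rule is ambiguous.

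**Conclusion.** The concern holds and must be fixed. As written, the rule has a rejection probability of 0.962 under the 20% null and 0.166 at 50%. The intended rule, 7 or more CRs of 17, has 0.0377 and 0.834 and agrees with the plan's own 0.04 and 83%. The conclusion rests on the figures in Section 7.2 alone: an exact one-sided binomial test, n = 17, and CR as the tested endpoint. It does not depend on whether 20% or 21% is taken as the null, since alpha stays below 0.05 in both cases (0.038 and 0.048). Confidence is high.

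**What to change.** Replace the sentence in Section 7.2 that states the rule with wording such as:

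> With 17 patients, H0 is rejected if 7 or more complete responses are observed (exact one-sided alpha 0.038 at a CR rate of 20%; power 83% at a CR rate of 50%). With 6 or fewer complete responses, H0 is not rejected. At the 21% single-agent benchmark the same rule has alpha 0.048.

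Keep 20% as the single formal null and give the 21% figure only as supporting information. Say complete responses, so that partial responses cannot be counted towards the cut-off. Make the change before the Phase 2 response data are analysed, and align the 15 in Section 2.1 with the 17 used here, because the rule is valid only for 17.

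The cost is one sentence in Section 7.2. Sample size and trial conduct do not change.

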7.3 Correlative Studies Statistical Analysis Plan

For each of the correlative studies, summary statistics and graphical displays will be provided over time, changes from baseline will be summarized similarly over time, and baseline levels and changes from baseline will be displayed by response over time.

8.0 MEDICAL Monitoring

It is the responsibility of the Principal Investigator to oversee the safety of the study at his/her site. This safety monitoring will include careful assessment and appropriate reporting of adverse events as noted above, as well as the construction and implementation of a site data and safety-monitoring plan detailed below. Adverse events are evaluated regularly by the principal investigator in conjunction with the research team. The Data Safety and Monitoring Committee (DSMC) will review the study regularly as designated by the Data Safety and Monitoring Plan. Medical monitoring will include regular assessments of the number and type of serious adverse events as well as events of Clinical Interest.

8.1 Data Monitoring Committee

This investigator-initiated study will be monitored by the Data Safety Monitoring Committee (DSMC) of the New York University (NYU) Perlmutter Cancer Center (PCC). The DSMC

operates based on the 2014 National Cancer Institute approved Charter. It is an existing and multidisciplinary committee (consisting of clinical investigators/oncologists, biostatisticians, nurses, and research administration staff knowledgeable of research methodology and design and in proper conduct of clinical trials) that is responsible for monitoring safety, conduct and compliance in accordance with protocol data monitoring plans for clinical trials conducted in the NYU Langone Health Perlmutter Cancer Center that are not monitored by another institution or agency. The DSMC reports to the Director of the NYU Langone Health PCC.

Per the NYU PCC Institutional Data Safety and Monitoring Plan, this phase I/II trial will be monitored by the DSMC quarterly (from the date the first patient is enrolled), at times of pre-specified response assessment, and at the completion of the study, prior to study closure. This review includes accrual data, subject demographics, and adverse events. Principal Investigators are required to attend the review of their studies. Additional interim reviews can be scheduled based on SAE reports, investigator identified issues, external information, etc. The DSMC will review safety data every 3 months.

External sites will be monitored and informed of other adverse events by the medical monitor within 7 days of toxicities and within 3 business days of SAE. Additional conference calls will be scheduled as indicated based on the recommendations from the medical monitor, and the Overall PI of this study.

Data and Safety Monitoring Plan:

The principal investigator will conduct bi-weekly meetings with the research team, to monitor toxicity while there are active patients. The study will be reviewed by the NYU Perlmutter Cancer Center Data and Safety Monitoring Committee (DSMC). The DSMC reviews all data for patient safety according to the DSMC policies. This review includes an examination of patient accrual, adverse events and study results. For phase I, dose finding trials, a review of toxicity after the first defined cohort is conducted to assure no DLTs are found before proceeding to the next cohort, per the protocol definition. If additional cohorts are required to establish the recommended dose for the extended safety cohort or phase II component of a phase I/II trial, these cohorts will be evaluated in a similar manner. By definition, dose finding cohort data will have to be confirmed or extended, by the trial definition, prior to proceeding to the next treatment group. Reviews will be done within 2-3 days of the complete cohort data set being available, even if not coinciding with a scheduled monthly meeting, so as to not delay study accrual. Once the recommended dose is established, further interim reviews will be performed at accrual points established by the protocol. All studies are required to be reviewed at least annually, regardless of their accrual status. Principal Investigators are required to attend the review of their studies.

All sites will participate in a bi-weekly teleconference to discuss all toxicities for all patients enrolled up to cycle 5 of therapy.

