2.0 TRIAL DESIGN

2.1 Trial Design

This is a Phase 1/2 open label study of the combination of pembrolizumab and lenalidomide and in patients with relapsed/refractory (RR) non-Hodgkin lymphoma (NHL) and Hodgkin lymphoma (HL).

Dose escalation will follow a standard 3+3 design. Patients will be treated in cohorts of 3 patients starting with Dose Cohort A with lenalidomide 15mg PO day 1-14 and pembrolizumab 200mg IV day 1, in cycles of 21 days, until disease progression or toxicity up to 24 months. The number of patients expected to be enrolled in the dose escalation study is 9 (up to 12 patients if unexpected toxicity is observed).

If 0 out of 3 patients at a particular dose level experiences a dose limiting toxicity (DLT) within Cycle 1 of treatment, if in Dose Cohort A (lenalidomide 15mg) dose escalation will proceed to cohort B (lenalidomide 20mg), if in Dose Cohort B, 3 additional patients will be added. If a DLT occurs in 0 of 6 patients enrolled on Dose Cohort B this will be deemed the Maximum Tolerated Dose (MTD).

If a DLT occurs in only 1 out of 6 patients enrolled at a particular dose level, dose escalation will occur, however, if this occurs on Dose Cohort B (lenalidomide 20 mg) or Dose Cohort Z (lenalidomide 10 mg), this will be deemed the Maximum Tolerated Dose (MTD). MTD is defined as the highest dose level at which < 33% of 6 patients experience a DLT.

[figure not shown]
If a DLT occurs in ≥ 2 of 3 patients or ≥ 2 of 6 patients treated on Dose Cohort A (lenalidomide 15mg), there will be a dose de-escalation to Dose Cohort Z (lenalidomide 10 mg).

[figure not shown]
If a DLT occurs in ≥ 2 of 3 patients or ≥ 2 of 6 patients treated on Dose Cohort B (lenalidomide 20 mg) or the preceding dose level will be declared the MTD if there were no more than 1 DLT in this previous cohort.

If a DLT occurs in ≥ 2 of 3 patients or ≥ 2 of 6 patients on Dose Cohort Z (lenalidomide 10mg), the trial will be discontinued and the expanded cohort will not be implemented.

Once the MTD has been determined, 15 additional patients with relapsed refractory HL will be treated in in the Phase II portion of this trial at the MTD.

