3.2 Secondary Objective(s) & Hypothesis

Objectives:

Phase 1: To estimate the ORR, (CR, PR), SD and progression free survival (PFS) for the combination within and across dose levels of lenalidomide

Phase 2: To estimate clinical benefit (including SD), the PFS and duration of response (DOR), for the combination. To confirm the safety of the combination.

Hypothesis:

Phase 1: We hypothesize that the novel immune platform of pembrolizumab and lenalidomide, will be active in RR HL and NHL patients.

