5.9 Clinical Criteria for Early Trial Termination

Early trial termination will be the result of the criteria specified below:

1. Quality or quantity of data recording is inaccurate or incomplete
2. Poor adherence to protocol and regulatory requirements
3. Incidence or severity of adverse drug reaction in this or other studies indicates a potential health hazard to subjects
4. Plans to modify or discontinue the development of the study drug

In the event of Merck decision to no longer supply study drug, ample notification will be provided so that appropriate adjustments to subject treatment can be made.

Product: Pembrolizumab and Lenalidomide
Protocol/Amendment No.: Version 3.1 July 18th, 2017

Trial Period:			Treatment Cycles ^a									End of Treatment	Post-Treatment			
			Screening (Visit 1)	Cycle 1 day 1	Cycle 1 day 8	Cycle 1 day 15	2	3	4	To be repeated beyond 8 cycles				Discon	Safety Follow-up	Follow Up Visits
5	6	7								8						
Scheduling Window (Days):	-28 to -1					± 3	± 3	± 3	± 3	± 3	± 3	± 3	At time of Discon	30 days post discon	Every 12 weeks	Every 12 weeks
Directed Physical Examination																
Vital Signs and Weight	X	X	X	X	X	X	X	X	X	X	X	X	X		X	X
Height	X															
ECOG Performance Status	X	X	X	X	X	X	X	X	X	X	X	X	X			
Pregnancy Test – Urine or Serum -HCG ^c	X	X			X	X	X	X	X	X	X	X	X			
PT/INR and aPTT	X	X						X								
Complete Blood Count with Differential	X	X	X	X	X	X	X	X	X	X	X	X	X		X	
Comprehensive Serum Chemistry Panel	X	X	X	X	X	X	X	X	X	X	X	X	X		X	
ESR	X				X	X	X	X	X	X	X	X	X		X	
Urinalysis	X	X			X	X	X	X	X	X	X	X	X		X	
T3, FT4 and TSH	X	X			X	X	X	X	X	X	X	X	X		X	
Tumor Imaging	X							X ^A					X		X	

Product: Pembrolizumab and Lenalidomide
Protocol/Amendment No.: Version 3.1 July 18th, 2017

Trial Period:			Treatment Cycles ^a										End of Treatment	Post-Treatment		
Treatment Cycle/Title:		Screening (Visit 1)	Cycle 1 day 1	Cycle 1 day 8	Cycle 1 day 15	2	3	4	To be repeated beyond 8 cycles				Discon	Safety Follow-up	Follow Up Visits	Survival Follow-Up
Scheduling Window (Days):		-28 to -1				± 3	± 3	± 3	± 3	± 3	± 3	± 3				
Archival or Newly Obtained Tissue Collection		X				X ^b							X			
Correlative Studies Blood Collection		X				X			X				X			

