7.0 STATISTICAL ANALYSIS PLAN

7.1 Phase I Statistical Analysis Plan

The primary objective of the Phase I portion of this trial is to identify the MTD (Phase II dose) which is the dose at which the estimated proportion of patients with DLTs is less than 0.33. The standard 3+3 design is employed. Patients will be treated in cohorts of 3 patients starting with Dose Cohort A with lenalidomide 15mg PO day 1-14 and pembrolizumab 200mg IV day 1, in cycles of 21 days, until disease progression or toxicity up to 24 months. The number of patients expected to be enrolled in the dose escalation study is 9 (up to 12 patients if unexpected toxicity is observed).

If 0 out of 3 patients at a particular dose level experiences a dose limiting toxicity (DLT) within Cycle 1 of treatment, if in Dose Cohort A (lenalidomide 15mg) dose escalation will proceed to cohort B (lenalidomide 20mg), if in Dose Cohort B, 3 additional patients will be added. If a DLT occurs in 0 of 6 patients enrolled on Dose Cohort B this will be deemed the Maximum Tolerated Dose (MTD).

If a DLT occurs in only 1 out of 6 patients enrolled at a particular dose level, dose escalation will occur, however, if this occurs on Dose Cohort B (lenalidomide 20 mg) or Dose Cohort Z (lenalidomide 10 mg), this will be deemed the Maximum Tolerated Dose (MTD). MTD is defined as the highest dose level at which < 33% of 6 patients experience a DLT.

If a DLT occurs in ≥ 2 of 3 patients or ≥ 2 of 6 patients treated on Dose Cohort A (lenalidomide 15mg), there will be a dose de-escalation to Dose Cohort Z (lenalidomide 10 mg).

If a DLT occurs in ≥ 2 of 3 patients or ≥ 2 of 6 patients treated on Dose Cohort B (lenalidomide 20 mg) or the preceding dose level will be declared the MTD if there were no more than 1 DLT in this previous cohort.

If a DLT occurs in ≥ 2 of 3 patients or ≥ 2 of 6 patients on Dose Cohort Z (lenalidomide 10mg), the trial will be discontinued and the expanded cohort will not be implemented.

Once the MTD has been determined, 17 additional patients with relapsed refractory HL will be treated in in the Phase II portion of this trial at the MTD.

While clinical benefit rates and other outcome rates for each dose cohort will be estimated, all of the summary of patient outcomes is descriptive.

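### Phase 2 has no quantified toxicity criterion and no planned toxicity estimate, and the accrual-based reviews promised in section 8.1 are defined nowhere

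*Combined protocol and SAP*

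**What the plan says.** **Phase 1.** Section 7.1 gives count-based DLT rules and this definition: "MTD is defined as the highest dose level at which < 33% of 6 patients experience a DLT". Section 5.3.1.3 defines a DLT by events in the first 21-day cycle.

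**Phase 2 objective.** Section 3.2 lists, among the Phase 2 secondary objectives, "To confirm the safety of the combination".

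**Phase 2 analysis.** Section 7.2 covers the CR rate with an exact interval, other response measures, dose and time on treatment, and Kaplan-Meier summaries. It contains no DLT count, no adverse-event summary and no toxicity threshold.

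**Monitoring after the dose is set.** Section 8.1 says "Once the recommended dose is established, further interim reviews will be performed at accrual points established by the protocol". It also says "The DSMC will review safety data every 3 months", allows extra reviews prompted by SAE reports or other concerns, and provides bi-weekly research-team meetings and bi-weekly all-site calls on toxicity. Section 5.9 lists as a ground for early termination: "Incidence or severity of adverse drug reaction in this or other studies indicates a potential health hazard to subjects".

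**Size.** Section 7.1 says "Once the MTD has been determined, 17 additional patients with relapsed refractory HL will be treated in in the Phase II portion"; section 2.1 says "Once the MTD has been determined, 15 additional patients with relapsed refractory HL". The trial summary and section 7.2 also use 17.

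**The concern.** The review step that section 8.1 attaches to the period after dose selection cannot be carried out as written, because the points it relies on do not exist in sections 2.1, 5.9, 7.1, 7.2 or 8.1. The 33% limit that governs dose selection is not applied again once Phase 2 opens, yet Phase 2 holds most of the patients treated at the chosen dose: 17 of 6 + 17 = 23, or 74%.

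Two things are at stake. First, if the selected dose is more toxic than Phase 1 suggested, no stated count or rate requires anyone to pause. Second, the trial has a Phase 2 safety objective but no planned estimate with which to answer it, so the only formal DLT evidence would be that from at most 6 patients per level in Phase 1.

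**Working it through.** **Inputs.** MTD definition: fewer than 33% of 6 (7.1). Phase 2 size: 17 (7.1, 7.2). DLT window: 21 days (5.3.1.3). Enrolment: 26 to 29 patients in 18 to 24 months (trial summary). The true DLT rates of 33%, 40% and 50% are assumptions: the plan's limit and two values above it.

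**1. The plan's own figures.**
- 1/6 = 16.7% is below 33% and 2/6 = 33.3% is not, so the definition means at most 1 DLT in 6.
- The only quantified Phase 2 rule concerns efficacy. With n = 17, P(X ≥ 7) is 0.038 at a CR rate of 20% and 0.834 at 50%, matching the stated alpha of 0.04 and power of 83%. (They match for rejection at 7 or more CRs; the different cut-off wording in 7.2 is a separate matter.) There is no corresponding toxicity figure to reproduce.

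**2. What 6 patients show.** Exact (Clopper-Pearson) 95% intervals:
- 0/6: 0% to 46%
- 1/6: 0.4% to 64%

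Both upper limits exceed 33%.

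**3. Chance that a level tested in 6 patients is accepted.** P(X ≤ 1) = (1−p)^6 + 6p(1−p)^5:
- p = 0.33: 0.090 + 0.267 = 0.36
- p = 0.40: 0.047 + 0.187 = 0.23
- p = 0.50: 0.016 + 0.094 = 0.11

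This assumes the usual expansion to 6 after 1 DLT in 3, which the text implies but does not spell out. Also, if cohort A shows 0/3 and cohort B then fails, the rule naming the preceding level as MTD could leave it resting on 3 patients, against a definition that speaks of 6. Those passages need reconciling.

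**4. Consequence if such a dose is accepted.** Expected cycle-1 DLTs in 17 patients are 17p: 5.6, 6.8 and 8.5 at 33%, 40% and 50%.

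**5. DLT data in the documents for this drug pair.** The myeloma study in the lenalidomide part of section 4.1.3 reports 3/13 at lenalidomide 25 mg (23%; exact 95% interval 5% to 54%) and none at 10 mg. This trial goes no higher than 20 mg. The myeloma patients also received dexamethasone. The data neither show nor exclude rates of 40% to 50%.

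**6. How often the DSMC would look.** Accrual per quarter runs from 3 × 26/24 = 3.3 to 3 × 29/18 = 4.8 patients. At an even 26 patients in 18 to 24 months, 17 patients take 17/26 × 18 = 11.8 to 17/26 × 24 = 15.7 months, or about 4 to 5 quarterly reviews.

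**7. What a planned estimate would give.** Illustrative exact 95% intervals:
- Phase 2 alone, 3/17: 4% to 43%
- pooled with 6 Phase 1 patients at the MTD, 4/23: 5% to 39%

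The pooled rate is biased low because the MTD was selected for having at most 1 DLT in 6. Given selection, the expected Phase 1 count is 6p(1−p)^5 / P(X ≤ 1). At p = 0.20 this is 0.393/0.655 = 0.60, so the pooled rate averages (0.60 + 3.4)/23 = 17.4%. At p = 0.40 it is 0.187/0.233 = 0.80, so the pooled rate averages (0.80 + 6.8)/23 = 33.0%.

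**The case against.** The strongest reply is that Phase 2 is closely watched. A reader might infer from the missing accrual points that it has no toxicity trigger at all, or that a too-toxic dose would simply run to full accrual. The documents do not support that. Section 5.9 makes the incidence or severity of adverse reactions a ground for termination. The DSMC reviews safety quarterly, roughly every 3 to 5 patients, and can meet sooner on SAE reports. The team meets bi-weekly on toxicity, and the all-site calls cover patients up to cycle 5, well past the DLT window. SAEs are reported within 24 hours, and sections 5.3.1.2 and 5.3.1.3 give patient-level rules. The undefined accrual points probably remove little practical review, and the sentence may be general institutional text.

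It is also fair to say that the 40% and 50% scenarios are unfavourable ones, which Phase 1 would usually reject, and that the myeloma data point to a lower rate, though imprecisely.

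All of this stands. It does not supply a number, an obligation to pause, the missing review points, or an analysis for the stated safety objective. A small single-arm Phase 2 may reasonably rely on committee judgement, but the protocol should then say so instead of pointing to points that it does not set.

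**Conclusion.** The point holds as a gap in specification. Phase 2 has no quantified toxicity criterion, its accrual-based reviews are undefined, and section 7.2 cannot answer the safety objective in section 3.2. It does not hold as a claim that Phase 2 is unmonitored or lacks any toxicity-based ground for stopping.

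The size rests on the MTD being set on 6 patients. On that basis the data leave true DLT rates up to 46% or 64% open, and a level with a true rate of 40% is accepted about one time in four (23%). These acceptance figures are conditional on 6 patients being tested at the level and are not the probability that this trial selects such a dose. How likely rates of 40% or more are cannot be judged from the documents. The missing estimate depends on none of these assumptions and is the clearest part of the finding.

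**What to change.** 1. **Section 7.2.** Apply the section 5.3.1.3 DLT definition to cycle 1 of every Phase 2 patient, state who is evaluable, and report the DLT rate with an exact 95% interval. Make Phase 2 alone the main estimate. Add, as support, the rate pooled with Phase 1 patients treated at the MTD, noting its downward selection bias and that Phase 1 also admits NHL.
2. **Section 8.1.** Either name the accrual points or replace the reference with the quarterly schedule already given there.
3. **Sections 7.2 and 8.1.** Have the sponsor and DSMC state whether a quantified Phase 2 toxicity criterion consistent with the 33% limit applies. If so, give its operating characteristics; if not, give the reason. No boundary is proposed here, and what follows a review remains for the DSMC.
4. **Sections 2.1 and 7.1.** Reconcile the Phase 2 size of 15 with 17, and the 6-patient MTD definition with the rule that could leave it resting on 3.

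The cost is wording and a short added analysis, using a committee that already meets quarterly; no extra patients are needed. If a quantified criterion is adopted, it brings some risk of a pause at an acceptable dose, which the operating characteristics should show.
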